### ***Analysis of all treatment-emergent adverse events***

The following TEAE summaries will be generated for the safety population.

- Overview of TEAEs, summarizing number (%) of patients with any:
  - TEAE,
  - Serious TEAE,
  - TEAE leading to death,
  - TEAE leading to permanent treatment discontinuation;
- All TEAEs by primary SOC, showing number (%) of patients with at least 1 TEAE, sorted by internationally agreed order of primary SOCs;
- All TEAEs by PT, showing number (%) of patients with at least 1 TEAE, sorted by decreasing incidence of PT in the SAR425899 0.20 mg group;
- All TEAEs by primary SOC, HLGT, HLT and PT, showing number (%) of patients with at least 1 TEAE, sorted by internationally agreed SOC order. The other levels (HLGT, HLT, PT) will be presented in alphabetic order;
- All TEAEs by primary SOC and PT, showing number (%) of patients with at least 1 TEAE, sorted by internationally agreed SOC order and decreasing incidence of PTs within a SOC in the SAR425899 0.20 mg group. This sorting order will be applied to all other similar tables, unless otherwise specified;
- Common TEAEs (PTs with an incidence  $\geq 3\%$  in any treatment group) by primary SOC, HLGT, HLT, and PT, sorted by internationally agreed order of SOCs. The other levels (HLGT, HLT, PT) will be presented in alphabetic order;
- All TEAEs regardless of relationship and related to IMP by primary SOC, HLGT, HLT, and PT, showing number (%) of patients with at least 1 TEAE, sorted by internationally agreed order of SOCs. The other levels (HLGT, HLT, PT) will be presented in alphabetic order;
- All TEAEs by maximal severity, presented by primary SOC and PT, showing number (%) of patients with at least 1 TEAE by severity (ie, mild, moderate, or severe), sorted by sorting order defined above;
- Kaplan-Meier curves will be provided, when appropriate, for the time to first onset of the following PTs: nausea and vomiting;

- Summaries of common TEAEs (PTs with an incidence  $\geq 3\%$  in any treatment group) will be provided as appropriate by primary SOC, HLGT, HLT, and PT and by demographic factors including gender (Male, Female), age group ( $<50$ ,  $\geq 50$  to  $<65$ ,  $\geq 65$  to  $<75$ ,  $\geq 75$  years of age), and race (American Indian or Alaska Native, Asian/Oriental, Black, Native Hawaiian or Other Pacific Islander, White, Other). SOC will be sorted by internationally agreed order and the other levels (HLGT, HLT, PT) in alphabetic order.
- Summaries of common TEAEs (PTs with an incidence  $\geq 3\%$  in any treatment group) will be provided as appropriate for SAR425899 treatment groups by primary SOC, HLGT, HLT, and PT and by anti- SAR425899 antibody status (Positive, Negative) during the TEAE period as necessary. SOC will be sorted by internationally agreed order and the other levels (HLGT, HLT, PT) in alphabetic order.

#### ***Analysis of all treatment emergent serious adverse event(s)***

- All treatment-emergent SAEs by primary SOC, HLGT, HLT, and PT, showing the number (%) of patients with at least 1 treatment-emergent SAE, sorted by the internationally agreed SOC order. The other levels (HLGT, HLT, PT) will be presented in alphabetical order.
- All treatment-emergent SAEs regardless of relationship and related to IMP, by primary SOC, HLGT, HLT, and PT, showing the number (%) of patients with at least 1 treatment-emergent SAEs, sorted by the internationally agreed SOC order. The other levels (HLGT, HLT, PT) will be presented in alphabetical order.

#### ***Analysis of all treatment-emergent adverse event(s) leading to treatment discontinuation***

- All TEAEs leading to treatment discontinuation, by primary SOC, HLGT, HLT, and PT, showing the number (%) of patients with at least 1 TEAE leading to treatment discontinuation, sorted by the internationally agreed SOC order. The other levels (HLGT, HLT, PT) will be presented in alphabetical order.

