1 FLOW CHARTS

1.1 GRAPHICAL STUDY DESIGN

* depending on the SAR425899/placebo dose regimen
 SAR425899 and matching placebo: low dose regimen = 0.06 (1 week) – 0.12 mg (25 weeks)
 mid dose regimen = 0.06 (1 week) – 0.12 (1 week) – 0.16 mg (24 weeks)
 and high dose regimen = 0.06 (1 week) – 0.12 (1 week) – 0.16 mg (1 week) – 0.20 mg (23 weeks)
 Liraglutide: 0.6 mg (1 week) – 1.2 mg (1 week) – 1.8 mg (24 weeks)

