8.1.1 SAR425899 or matching placebo (solution for injection)

- Pharmaceutical form: SAR425899 solution for injection or matching placebo are supplied as cartridges containing 3 mL solutions for injection containing:
 - For SAR425899: SAR425899 at a concentration of 0.5 mg/mL in sodium dihydrogen phosphate dihydrate, di-sodium hydrogen phosphate dodecahydrate, sodium chloride, m-cresol, HCL/NaOH and water for injection,
 - For SAR425899 placebo: sodium dihydrogen phosphate dihydrate, disodium hydrogen phosphate dodecahydrate, sodium chloride, m-cresol, HCL/NaOH and water for injection.
- Route and method of administration: SC injection using the pen-type injector (Tactipen®).
- Dose of IMP per administration:
 - For SAR425899 and matching placebo, patients will be randomized to following dose regimen :
 - Low dose: 1 step weekly dose increase (if no significant tolerability issues [example, nausea and vomiting] are observed): 0.06 mg ie, 12U – 0.12 mg ie, 24U (0.12mg ie, 24U for 25 weeks).
 - Mid dose: 2 step weekly dose increase (if no significant tolerability issues [example, nausea and vomiting] are observed): 0.06 mg ie, 12U – 0.12 mg ie, 24U – 0.16 mg ie, 32U (0.16 mg ie, 32U for 24 weeks).
 - High dose: 3 step weekly dose increase (if no significant tolerability issues [example, nausea and vomiting] are observed): 0.06 mg ie, 12U – 0.12 mg ie, 24U – 0.16 mg ie, 32U – 0.20 mg ie, 40U (0.20 mg ie, 40U for 23 weeks).
- Timing: doses of SAR425899 and placebo should be injected in the morning at the same time every day except on clinic visit days.
- On clinic visit days, SAR425899 and placebo injection time should be after blood tests/ECG measurement time in the morning and be coordinated with the meal test/PK sampling time.

If the target dose is not tolerated, the study treatment can be decreased. Another attempt for dose increase may take place within 4 weeks and before Week 8 of treatment. Then, if the patient cannot reach or tolerate the target dose, he/she remains at the lower dose. If he/she cannot tolerate the lower dose, end of treatment assessments are done. Then, the patient will be discontinued from IMP but continues in the study and is followed up according to the study procedures as specified in this protocol (except for the post-treatment follow-up), up to the scheduled date of study completion. After Week 8, if the dose is no longer tolerated, final on-treatment visit assessments are done and the patient is discontinued from the IMP.

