8.1.3 Injection device and training

Tactipen injector (specifically labelled for the use of the study) with needles will be provided to each patient separately from the cartridges kits. Cartridges will have to be assembled in the Tactipen by the patient. Handling procedure, detailed storage instructions of the pen-type injector and SC injection technique will be provided in a specific manual.

For both Tactipen and liraglutide pen, before starting the first dosing and repeat as often as required, the patients will be trained on site by the study staff to use the injector pens and to perform the SC injection (see the flow chart [Section 1.2](#)). Pen-device or related issues (malfunctions) should be reported to the Sponsor by the means of a procedure on product technical complaint (PTC) forms, which will be described in a separate manual.

Training on self-measured plasma glucose (SMPG) technique will be performed and repeated as needed throughout the study.

Liraglutide is a marketed product, it will be administrated as per local labelling (such as SmPC in the European Union or PI in the US), except for the time of injection in order to be consistent with the study request. The first administration will be done under clinical staff supervision and it will have to follow the PTC process.

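### No planned safety table counts adverse events that led to a dose reduction, and stepped-down patients are regrouped by their Week 8 dose, so the tolerability dose-response before Week 8 may be understated or distorted

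*SAP*

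**What the plan says.** **Dosing.** Protocol 8.1.1, on SAR425899 and its placebo, states: "If the target dose is not tolerated, the study treatment can be decreased". One further attempt to increase the dose is possible before Week 8. "Then, if the patient cannot reach or tolerate the target dose, he/she remains at the lower dose". IMP stops only if the lower dose also fails. Later the rule changes: "After Week 8, if the dose is no longer tolerated, final on-treatment visit assessments are done and the patient is discontinued from the IMP". Protocol 1.1 gives the titration ladder. Below target there is one level in the 0.12 mg arm (0.06), two in the 0.16 mg arm (0.06, 0.12) and three in the 0.20 mg arm (0.06, 0.12, 0.16).

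**Tables.** SAP 2.4.5.2 plans all TEAEs by SOC and PT, common TEAEs, related TEAEs, TEAEs by maximal severity, AESIs, and Kaplan-Meier curves for first nausea and vomiting. Stopping is covered by an overview line, "TEAE leading to permanent treatment discontinuation", by the table "All TEAEs leading to treatment discontinuation, by primary SOC, HLGT, HLT, and PT", and by the Kaplan-Meier plots of IMP discontinuation in SAP 2.2.

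**Dose reduction.** The investigator records the action taken with IMP for each AE (Protocol 10.4.3). The SAP prints it only in the AE listings.

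**Grouping.** Under SAP 2.3.2 a patient randomised to SAR425899 is analysed for safety under the dose taken from the Week 8 visit. A patient who stops before Week 8 stays in the randomised arm.

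**The concern.** Two features act together. First, a patient who fails the target dose and settles on a lower one has had a dose-limiting event, but enters none of the discontinuation outputs. The number of levels available for this rises with the target dose. Second, the tables that do count the event move it: a patient who fails 0.20 mg and stays on 0.12 mg takes those events into the 0.12 mg column.

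Safety is a main secondary objective of this three-dose study (Protocol 5.2), and Protocol 8.1.1 itself names nausea and vomiting as reasons not to escalate. A reader comparing doses needs to know how many patients in each randomised arm could not stay on the assigned dose because of an AE. No planned table says so.

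The compliance summaries do not clearly fill the gap. Under SAP 2.4.3.2 the planned dose is the intended dose entered in the eCRF, which is not stated to be the randomised target. A patient kept on a lower intended dose may count as fully compliant.

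**Working it through.** The plan states no tolerability rate, so there is no figure of its own to reproduce. The HbA1c power calculation is not involved.

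**Inputs from the documents:** 60 patients per SAR425899 arm (Protocol 11.1); the ladder (Protocol 1.1); the stopping rule (Protocol 8.1.1); the grouping rule (SAP 2.3.2).

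**Inputs assumed:** 10/20/30/40% of patients do not tolerate 0.06/0.12/0.16/0.20 mg. A patient who fails one level fails all higher ones. All of this happens before Week 8.

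**Step 1. Target-dose intolerance by randomised arm.** 60 × 0.20 = 12, 60 × 0.30 = 18, 60 × 0.40 = 24, that is 20/30/40%.

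**Step 2. Step-down to any lower level.**

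| Randomised arm | Stopped | On 0.06 | On 0.12 | On 0.16 | On 0.20 |
|---|---|---|---|---|---|
| 0.12 mg | 6 | 6 | 48 | – | – |
| 0.16 mg | 6 | 6 | 6 | 42 | – |
| 0.20 mg | 6 | 6 | 6 | 6 | 36 |

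SAP 2.3.2 columns (stopped in that arm plus all on that dose):
- 0.12 mg: 6 + 48 + 6 + 6 = 66
- 0.16 mg: 6 + 42 + 6 = 54
- 0.20 mg: 6 + 36 = 42
- The 18 patients on 0.06 mg match no treatment group and are kept apart here.

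Discontinuation as tabulated: 6/66, 6/54, 6/42 = 9.1/11.1/14.3%.

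Patients with a dose-limiting event (stopped, or stepped down into the column): (6 + 12)/66, (6 + 6)/54, 6/42 = 27.3/22.2/14.3%. The order is the reverse of step 1.

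If the 18 patients on 0.06 mg are returned to their randomised arms, the columns are 72, 60 and 48. Discontinuation is 6/72, 6/60, 6/48 = 8.3/10.0/12.5%. Dose-limiting events are 24/72, 18/60, 12/48 = 33.3/30.0/25.0%, still reversed.

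**Step 3. One step down only.**

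| Randomised arm | Stopped | On 0.06 | On 0.12 | On 0.16 | On 0.20 |
|---|---|---|---|---|---|
| 0.12 mg | 6 | 6 | 48 | – | – |
| 0.16 mg | 12 | – | 6 | 42 | – |
| 0.20 mg | 18 | – | – | 6 | 36 |

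Columns: 6 + 48 + 6 = 60; 12 + 42 + 6 = 60; 18 + 36 = 54. Discontinuation: 6/60, 12/60, 18/54 = 10/20/33%. Dose-limiting events: (6 + 6)/60, (12 + 6)/60, 18/54 = 20/30/33%. The order is kept, but discontinuation is below target-dose intolerance in every column.

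**Step 4. Dependence on the tolerance model.** Suppose instead that each lower level fails independently with probability q, and patients may use every level. Discontinuation by randomised arm, before any regrouping, is then 0.20q, 0.30q², 0.40q³:
- q = 0.5: 10/7.5/5%, order reversed
- q = 0.7: 14/14.7/13.7%, about flat
- q = 0.9: 18/24.3/29.2%, order kept

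**The case against.** The other side has good points.

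- **All TEAEs are counted.** A reader might infer that an AE counts only if it ends treatment. That is wrong: nausea managed by a step-down enters the all-TEAE, severity and Kaplan-Meier outputs. But those outputs do not show whether an event was dose-limiting, and they use the same Week 8 grouping.
- **The discontinuation table can still show a dose-response.** A reader might infer that it must be flat. With step-down to any level, stops in the illustration are 10/10/10% by randomised arm, but the planned table is not built that way. After the SAP grouping it shows 9/11/14%, or 10/20/33% with one step. Understatement and possible distortion stand; inability to show an ordering does not.
- **One step may be the more natural reading.** Protocol 8.1.1 refers to a single lower dose. Protocol 10.1.3, however, foresees re-escalation over one, two or three weeks depending on the decreased dose. The point stays open.
- **Later intolerance is captured.** For 18 of the 26 weeks no step-down is allowed, so intolerance leads to discontinuation and reaches the table.
- **The rates are assumed, and nothing ranks the discontinuation table above the others.** Both are true. The safety analysis is described as essentially descriptive.
- **Liraglutide.** A reader might infer an unequal chance to step down against liraglutide. The documents do not establish it. The liraglutide section has no step-down rule, but Protocol 8.1.3 states "Liraglutide is a marketed product, it will be administrated as per local labelling", and that labelling is not in the documents. SAP 2.3.2 keeps liraglutide patients in their arm whatever amount they take.

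**Conclusion.** The concern holds as a gap in the tables. AE-driven dose reductions are recorded and listed but not tabulated. Before Week 8 these patients are missing from the discontinuation outputs, and their earlier events move into lower-dose columns, while early stoppers stay where they were randomised. The safety tables may therefore understate or distort the tolerability dose-response in that period.

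The size is unknown. Under the assumed 10/20/30/40%, target-dose intolerance of 20/30/40% appears as discontinuation of 9/11/14% (any level) or 10/20/33% (one step). Patients with a dose-limiting event appear as 27/22/14% (any level), or 20/30/33% (one step), which is close to the truth. The distortion thus depends on how many steps down are used and how well lower doses are tolerated. Neither can be read from the planned tables. No sample size or alpha figure is affected. This is a worthwhile, inexpensive improvement and does not invalidate the safety analysis.

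**What to change.** In SAP 2.4.5.2, beside the table of TEAEs leading to discontinuation, add descriptive tables by **randomised** arm, split before and after Week 8, of n (%) of patients with:

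- (a) a TEAE leading to dose reduction, taken from the action-taken-with-IMP field;
- (b) a TEAE leading to permanent discontinuation;
- (c) either.

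That the field has a dose-reduced code is an inference. If it has none, derive (a) from the administered doses that Protocol 10.2.1 requires as source data. Differences from placebo with 95% CI are optional and descriptive. Show liraglutide alongside, without claiming that its step-down opportunity differed. State that these tables are by randomised arm, because SAP 2.3.2 groups the other safety tables differently.

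Protocol 8.1.1 and 10.1.3 should also be reconciled on how many steps down are possible. No dosing rule is proposed here.

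The cost is SAP wording and two or three extra tables. The composite mixes reductions with stops, so its components are shown separately.

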#### **Analysis of AESI**

The number (%) of patients with specific AESIs will be summarized by category (as identified in [Section 2.1.4.2](#)) and PT, and sorted by decreasing incidence in the SAR425899 0.20 mg group.

All AESI events reported by the Investigators will be listed.

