6 STUDY DESIGN

6.1 DESCRIPTION OF THE STUDY

This is a multicenter, multinational, randomized, placebo-controlled, 7-arm parallel-group Phase 2 study. The study is double-blind with regard to SAR425899 and placebo treatments. It is open-label with regard to liraglutide comparative treatment. The volume of investigational medicinal product (IMP; ie, dose of SAR425899 or matching placebo) is not blinded.

Patients will be randomized into 1 of the 7 treatment arms:

- 3 SAR425899 treatment arms receiving 3 dose levels (60 patients per arm).
- 3 corresponding SAR425899 placebo treatment arms receiving 3 dose levels (10 patients per arm, 30 patients total).
- 1 active comparator arm receiving 1.8 mg liraglutide (60 patients).

For the biostatistical analyses, data from the 3 SAR425899 placebo arms will be pooled into 1 placebo group.

Patients will be stratified by screening visit HbA_{1c} (<8 % versus ≥8 %) and Visit 4 (Day 1) body mass index (BMI: <35.0 kg/m² versus ≥35.0 kg/m²).

Treatment doses and dose increase process are described in [Section 8.1](#).

In case of fasting plasma glucose (FPG) or HbA_{1c} (assessed by central laboratory) above predefined thresholds and if no reasons can be found for insufficient glucose control, it is recommended to add a rescue therapy (please see rescue therapy in [Section 8.8.2](#)).

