9.2.2.5 Vital signs and physical examination

Clinical safety will be assessed by:

- Physical examination
- Vital signs (systolic and diastolic blood pressure, heart rate).
 - Blood pressure (mmHg) should be measured in sitting position,
 - Heart rate (bpm) will be measured in supine position at the time of the measurement of blood pressure (predose on Weeks -3, -1, 0, 2, 4, 8, 14, 20 and 26),
 - Height without shoes only at screening.

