#### **AESI include:**

- Pregnancy
- Symptomatic overdose
- Alanine aminotransferase (ALT) increase >3X upper limit of normal (ULN) (per related decision chart in Appendix C of protocol)
- prolongation of QTc interval  $\geq 500$  ms (automatic measurement and confirmed by a manual reading by the Investigator or a physician delegated by the Investigator using the Fridericia formula for correcting QT)
- sinus tachycardia (defined as confirmed sinus tachycardia [heart rate >100 bpm] in supine position reported at more than 2 visits) and associated with a concomitant increase, from baseline, in heart rate of  $\geq 15$  beats per minute
- Severe allergic or allergic-like reaction (except local reactions at site of injection)
- Calcitonin  $\geq 20$  pg/mL: events recorded on the AE form for increased calcitonin and its associated complementary form.
- Amylase or lipase >2 x ULN
- Metabolic acidosis

Note that all AESI are identified by the corresponding AECAT variable in the AE raw dataset and/or other specific form as listed in the table below.

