**Table 3 - Summary of AESI reporting instructions**

Event category	Reporting timeframe	Specific events in this category	Case Report Form completion		
			AE form	Safety Complementary Form	Other specific forms
Adverse Event of Special Interest	Expedited (within 24 hours)	Pregnancy	Yes	Yes	Yes
		Symptomatic overdose	Yes	Yes	Yes
		Increase in alanine transaminase (ALT)	Yes	Yes	Yes
		Prolongation of QTc interval (automatic measurement) $\geq 500$ ms	Yes	Yes	No
		Persistence of sinus tachycardia per definition in Section 2.1.4.2 and associated with a concomitant increase, from baseline, in heart rate of $\geq 15$ beats per minute	Yes	Yes	No
		Severe allergic or allergic-like reaction (except local reactions at site of injection)	Yes	Yes	Yes
		Calcitonin $\geq 20$ pg/mL	Yes	Yes	Yes
		Amylase/lipase $> 2 \times \text{ULN}$	Yes	Yes	Yes
		Metabolic acidosis	Yes	Yes	No

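### The persistent sinus tachycardia AESI is counted from investigator-filed forms alone; add a cross-check count from the recorded supine heart rates

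*SAP*

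**What the plan says.** SAP 2.4.5.2 (Analysis of AESI) states: "The number (%) of patients with specific AESIs will be summarized by category", and by preferred term, using the cases identified in SAP 2.1.4.2. That section says that "all AESI are identified by the corresponding AECAT variable in the AE raw dataset and/or other specific form". It defines this event as "sinus tachycardia (defined as confirmed sinus tachycardia [heart rate >100 bpm] in supine position reported at more than 2 visits", together with a rise of at least 15 bpm from baseline. SAP Table 3, in the row beginning "Persistence of sinus tachycardia per definition in", requires the AE form and the Safety Complementary Form and has No under other specific forms. Neither document derives this AESI from recorded heart rates.

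The measurements exist. Under Protocol 9.2.2.5, heart rate "will be measured in supine position at the time of the measurement of blood pressure", and the post-baseline visits are Weeks 2, 4, 8, 14, 20 and 26. Under Protocol 9.2.2.6.1, supine 12-lead ECGs are assessed by the investigator, post-baseline at Weeks 4, 14 and 26.

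On blinding, Protocol 6.1 says of the study: "It is open-label with regard to liraglutide comparative treatment". Protocol 8.3.1 keeps SAR425899 versus placebo blinded but leaves the dose level known.

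**The concern.** The persistence rule spans at least three visits, several of them six weeks apart (Weeks 8, 14, 20 and 26). A site has to notice the third high reading, look back at the earlier ones, compare them with baseline and then file the event. A patient who meets the numbers but is not filed is absent from the table, and no planned output would show the omission.

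Heart-rate change is named in a main secondary safety objective, and persistent tachycardia is one of the project-specific AESIs in Protocol 10.4.1.3. Missed cases would understate the AESI in whichever group they occur. Sites also know the dose level and the liraglutide assignment, so attention to heart rate could differ between those groups.

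**Working it through.** The plan states no expected rate or precision for this AESI, so there is no figure of its own to reproduce. The check is a trace of the documents followed by simple arithmetic.

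**1. How a case enters the count.** SAP 2.4.5.2 points to 2.1.4.2, which points to the AE category variable and/or another specific form. Table 3 has no other specific form for this event. The only route left is the AE record and its Safety Complementary Form, both started by the investigator.

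**2. When a record is created.** Protocol 10.4.3 makes a vital-sign or ECG abnormality an AE only if it is symptomatic, needs treatment or consultation, affects IMP dosing, is serious, or is an AESI. In a patient without symptoms, the first two readings above 100 bpm need leave no AE record. The duty to notify within 24 hours (Protocol 10.4.5) can act only once the pattern is recognised. Protocol 8.3.1 and 8.8.2 describe central-laboratory alerts for FPG and HbA1c; no alert is described for heart rate.

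**3. What the scheduled data can verify.** More than 2 visits means at least 3 of the 6 post-baseline supine readings. The rate and the rise can be checked from these. Sinus rhythm cannot: if each qualifying visit needed a scheduled ECG, all 3 post-baseline ECGs would have to qualify.

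**4. What the other heart-rate analyses give.**
- SAP 2.4.5.5 and 2.4.5.6: summaries and changes by visit, and the incidence of at least one potentially clinically significant abnormality (PCSA).
- SAP 2.4.5.7: 24-hour and night-time averages, in the Holter subset of up to 50% of patients.
- None of these is a count per arm of patients with a high rate at three or more visits.

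**5. A precedent in the same SAP.** Calcitonin of at least 20 pg/mL is also an AESI. SAP 2.4.5.4 tabulates calcitonin from laboratory values as well, with a cut-point at 20 ng/L, which the SAP equates to pg/mL.

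**6. Size of one missed case** (planned group sizes, SAP 1.1):
- Arm of 60: 1/60 = 1.7 percentage points.
- Pooled placebo, 30: 1/30 = 3.3 percentage points.

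**7. Illustration of under-recording (assumed values).** Suppose 10% of an arm qualifies: 0.10 × 60 = 6 patients. If 50% to 80% are filed, the table shows 6 × 0.5 = 3 to 6 × 0.8 = 4.8 patients, that is 5% to 8%.

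**8. Illustration of unequal recording (assumed values, no true difference).** Take a true rate of 10% everywhere. Placebo patients are recorded with the probability of their own dose volume, since active and placebo are blinded within a volume, and the three volumes contribute equally (10 patients each). Cases counted per 60 = 60 × 0.10 × recording probability.

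| Recording probability, 0.12 / 0.16 / 0.20 mg / liraglutide | Counted per 60 | Pooled placebo | 0.20 mg : placebo | 0.12 mg : liraglutide |
|---|---|---|---|---|
| equal (1.0) | 6.0 / 6.0 / 6.0 / 6.0 | 10.0% | 1.00 | 1.00 |
| 0.6 / 0.7 / 0.8 / 0.9 | 3.6 / 4.2 / 4.8 / 5.4 | 7.0% | 1.14 | 0.67 |
| 0.5 / 0.6 / 0.8 / 1.0 | 3.0 / 3.6 / 4.8 / 6.0 | 6.3% | 1.26 | 0.50 |

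In the last row, pooled placebo is 10% × (0.5 + 0.6 + 0.8)/3 = 6.3%, and the ratios are 0.8/0.633 = 1.26 and 0.5/1.0 = 0.50. The ratios do not depend on the assumed true rate. The dose-to-liraglutide comparison moves most; a dose against pooled placebo moves less.

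**The case against.** The strongest case against has five parts.

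- **The definition is not purely numeric.** It requires confirmed sinus tachycardia, and a vital-signs rate shows neither confirmation nor rhythm. A list built from rates alone may include patients who were correctly not reported. This stands: the derived count can only be a cross-check.
- **Measured heart rate is analysed in every group.** The main secondary objective concerns heart-rate change by ECG and Holter, and SAP 2.4.5.5 to 2.4.5.7 need no AE form. This stands, and it limits the point to the one AESI.
- **Individual profiles are listed.** SAP 2.4.5.5 plans a listing over time for each patient with at least one PCSA, so some persistent cases could be found by hand. This stands in part: it gives no count by arm. The thresholds are in SAP Appendix A, which was not in the text available for this review, so the overlap with 100 bpm and 15 bpm could not be checked.
- **Reporting is mandatory and monitored.** Protocol 10.4.1.3, 10.4.3 and 10.4.5 require it, 13.2 puts AESI reporting under monitoring, and 13.4 lets the sponsor query entered data. These safeguards lower the chance of omission. None of them specifies a comparison of AESI records with the heart-rate series.
- **Active versus placebo is blinded at each dose volume.** Knowledge of assignment cannot drive reporting there, and the liraglutide comparison is exploratory. This stands, and it leaves dose-versus-dose and liraglutide comparisons as those mainly exposed.

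**Conclusion.** The point holds in a limited form. The persistent-tachycardia AESI count rests on investigator forms alone, its numeric elements could be verified from data already scheduled, and no such check is planned. Under-recording would understate this AESI by 1.7 points per missed case in an arm of 60 and by 3.3 points in the placebo group. The number of missed cases is unknown; the 10% incidence and all recording probabilities above are assumptions with no source in the documents. The 60 and 30 are planned randomised numbers, and the safety groups may differ slightly.

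A reader might infer that the trial's heart-rate signal depends on AE reporting, that the scheduled heart rates by themselves define the event, or that knowledge of treatment biases the comparison with placebo. The documents support none of these: measured heart rate is analysed separately, the definition includes sinus rhythm, and active and placebo are blinded within each volume. Differential recording is a risk, not a demonstrated bias. The AESI analysis is descriptive, and no test, estimand or error rate depends on it. This is a cheap improvement, not the correction of an error.

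**What to change.** In SAP 2.4.5.2 (Analysis of AESI):

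- Add a supportive row labelled 'numeric criteria met (sinus rhythm not confirmed)'. It gives, per treatment group, the number and percentage of patients with supine heart rate above 100 bpm at more than 2 visits in the TEAE period and a rise of at least 15 bpm from baseline, derived from the vital-signs data. State whether the rise must be present at each qualifying visit.
- Show this row beside the investigator-reported AESI.
- List the patients who meet the numbers but have no AESI record, with any ECG rhythm finding.
- Reconcile the two before database lock.

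The cost is one derived flag, one table row and one listing from data already collected. Sample size, power, alpha and clinical management do not change. The downside is that some listed patients may have non-sinus or unconfirmed tachycardia, so the row supports the reported AESI and does not replace it.
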